7.5 ELECTROCARDIOGRAMS

ECG measurements are obtained at the screening visit and Week 12. Single 12-lead ECG will be obtained using an ECG machine that may automatically report heart rate, PR, QRS, QT, and/or Fridericia's corrected QT (QTcF) intervals. If any of these parameters are not automatically reported, they may be measured or calculated.

The ECG assessment values at each visit and change from baseline to each visit will be summarized and shift table using the normal/abnormal classification to compare baseline to the post-baseline visit values will be provided. In addition, a by-subject listings, which includes treatment group, subject ID, ECG date/time, test name, test result and ECG interpretation (eg, clinical interpretation, normal abnormal, not clinically significant, abnormal, clinically significant) will be presented. If any clinically significant ECG measurement occurs, it will be recorded as an AE.

8 OTHER ANALYSES

8.1 QUALITY OF LIFE(QOL)

The Inflammatory Bowel Disease Questionnaire (IBDQ) is a self-administered, disease-specific Health-Related Quality of Life (HRQOL) instrument for patients with IBD. [11] The IBDQ covers 4 dimensions: bowel symptoms (10 items, questions 1, 5, 9, 13, 17, 20, 22, 24, 26, and 29), systemic symptoms (5 items, questions 2, 6, 10, 14 and 18), emotional function (12 items, questions 3, 7, 11,15, 19, 21, 23, 27, 30, 31 and 32), and social function (5 items, questions 4, 8, 12, 16, and 28). Items are scored on a 7-point Likert scale, for a total global score in the range 32 to 224 (with higher scores indicating better HRQOL).

IBDQ scores will be collected at Week 0 Visit, Week 6 Visit, and Week 12 Visit. Summary statistics of the absolute and change from baseline scores for IBDQ total score and each subscale score will be displayed by treatment group and visit.

IBDQ Scores will be calculated as follows:

- The question on the same day of measurement will be used for calculation of each subscore and total score.
- For each subscore, sum of the questions will be round off to the first decimal place.
- IBDQ total score: sum of all questions and round off to the first decimal places.
- The value of each question after imputing missing data will be used for the calculation of each subscore.

The instructions on how the IBDQ score is calculated in the presence of missing or incomplete information is provided below with detailed scenarios given in Table 9. Rules for handling missing data:

1. If no response is given for a particular question and only one response per dimensional score is missing, impute the missing value to be equal to the mean score for that other item of the subscore
2. If two or more questions are unanswered for a particular domain, then the subscore will be set to missing.

If after steps 1 and 2, more than 4 questions are missing for the full IBQD, then the total IBDQ will be set to missing.

Table 9 IBDQ Missing Data Instructions

	Number of Missing Values				Comments/Actions
	Subscore 1	Subscore 2	Subscore 3	Subscore 4	
Scenario A	0	0	0	0	We can compute 4 subscores and the full IBDQ
Scenario B	1	0	0	0	We can compute both the full IBDQ and the 4 subscores, by replacing the missing value with the average mean (computed on the data available for its own subscore)
Scenario C	1	1	1	1	We can compute both the full IBDQ and the 4 subscores, by replacing the missing value with the average mean (each one computed on the data available for its own subscore)
Scenario D	2	0	0	0	We can compute the full IBDQ by replacing the 2 missing values with the average mean (computed on the data available for its own subscore). We can compute only 3 subscores.
Scenario E	2	1	0	1	We can compute the full IBDQ by replacing the missing values with the average mean (each one computed on the data available for its own subscore). We can compute only 3 subscores.
Scenario F	2	1	1	1	We cannot compute the full IBDQ (more than 4 missing values). We can compute only 3 subscores.
Scenario G	2	2	0	0	We cannot compute the full IBDQ because in more than one subscore there are 2 missing values (even though the total missing value is not exceeding 4). We can compute only 2 subscores.
Scenario H	0	0	3	0	We cannot compute the full IBDQ because there is one subscore with more than 2 missing values. We can compute only 3 subscores.

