### **6.4.5 Quality of Life (QoL)**

Subjects will be asked to complete the Inflammatory Bowel Disease Questionnaire (IBDQ) at visits specified in [Section 6.1.1](#) to measure disease specific quality of life (QoL). The questionnaires completed by subjects will serve as the source documents for this study.

The IBDQ is a self-administered 32-item questionnaire that evaluates QoL across 4 dimensions: (1) Bowel – symptoms related to primary bowel disturbance, (2) Systemic symptoms, (3) Emotional function, and (4) Social function. The response to each question can range from 1 to 7, with 1 indicating severe problem and 7 indicating normal health. The total IBDQ is computed as the sum of the responses to the individual IBDQ questions. The total score can range between 32 to 224 with higher scores indicating a better QoL ([Guyatt 1989](#)).

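### SAP section 8.1 gives the IBDQ emotional function domain 12 items but lists 11, leaving question 25 in no domain

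*SAP*

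**What the plan says.** SAP section 8.1 assigns IBDQ questions to four domains in a single sentence:

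- The domain at issue is given as "emotional function (12 items, questions 3, 7, 11,15, 19, 21, 23, 27, 30, 31 and 32".
- The entry for the bowel domain reads "bowel symptoms (10 items, questions 1, 5, 9, 13, 17, 20, 22, 24, 26, and 29".
- For the systemic domain the SAP has "systemic symptoms (5 items, questions 2, 6, 10, 14 and 18".
- The last of the four domains appears as "social function (5 items, questions 4, 8, 12, 16, and 28".

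It then gives the scale of the whole instrument: "Items are scored on a 7-point Likert scale, for a total global score in the range 32 to 224". Protocol section 6.4.5 agrees on the number of items ("The IBDQ is a self-administered 32-item questionnaire that evaluates QoL across 4 dimensions") and on item scoring ("The response to each question can range from 1 to 7").

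The rest of SAP section 8.1 relies on this assignment. Each subscore is the sum of its domain's questions and is summarised as a value and as a change from baseline, with collection at Weeks 0, 6 and 12. A single unanswered question in a domain is replaced by the mean of that domain's other items. Two or more unanswered questions set the subscore to missing. Table 9 uses the number missing in each subscore to decide which scores can be computed. The total has its own definition, the sum of all questions, and Protocol section 6.4.5 defines it the same way.

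**The concern.** The sentence is the only place in either document that says which question belongs to which domain, so it serves as the scoring specification. Its stated count and its list disagree. A programmer who codes the list leaves question 25 out of the emotional function subscore. The programmer also has no domain in which to place question 25 when it is unanswered. What is at stake is a reported quality-of-life subscore, and the handling of missing items that involve question 25 or the emotional function domain.

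**Working it through.** **Inputs.** Stated counts and question lists: SAP 8.1. Items scored 1 to 7 and 32 items in all: Protocol 6.4.5. Total range 32 to 224: SAP 8.1 and Protocol 6.4.5.

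**The plan's own figure.** The stated counts give 10 + 5 + 12 + 5 = 32 items. The total then runs from 32 × 1 = 32 to 32 × 7 = 224, which reproduces the stated range. The stated counts are therefore consistent with the rest of the plan.

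**Counting the lists.** For n items the range is n to 7n.

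| Domain | Items stated | Items listed | Range from stated count | Range from list |
|---|---|---|---|---|
| Bowel | 10 | 10 | 10–70 | 10–70 |
| Systemic | 5 | 5 | 5–35 | 5–35 |
| Emotional | 12 | 11 | 12–84 | 11–77 |
| Social | 5 | 5 | 5–35 | 5–35 |
| All | 32 | 31 | 32–224 | 31–217 |

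The 31 listed numbers are all different. Removing them from 1 to 32 leaves only question 25. Emotional function is the only domain that is short, and it is short by one.

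**Effect on the subscore, complete data.** Let E12 be the 12-item subscore, E11 the subscore from the list and q the answer to question 25. Then E11 = E12 − q. Since q lies between 1 and 7, the listed version is 1 to 7 points low at each visit.

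**Effect on its change from baseline.** The error is −(q at the visit − q at baseline). It is zero where the two answers are equal, and otherwise at most 7 − 1 = 6 points in either direction.

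**Effect on the total, complete data.** The written rule sums all questions, so question 25 is included and the total is correct.

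**Effect when items are missing.**

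- *Only question 25 unanswered.* As a 12th emotional item it would be replaced by the mean of the other 11 (Table 9, Scenario B). Under the list it has no domain mean, so the SAP gives no value for it in the total, while the emotional subscore appears complete.
- *Questions 25 and 27 unanswered.* With 12 items, two are missing and the emotional subscore is set to missing. Under the list only one is counted, so the subscore is imputed and reported.
- *Question 25, one other emotional item and two bowel items unanswered.* With 12 items, two domains have two missing each, and Scenario G bars the total. Under the list the emotional count is one, and Scenario G is not triggered.
- *Another emotional item unanswered, question 25 answered.* The imputed value is m, the mean of 10 items, instead of (10m + q)/11. The difference is (q − m)/11 in absolute size, at most 6/11 = 0.55 points, and it carries into the total.

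The limit of more than four missing questions applies to the whole questionnaire, so question 25 still counts there.

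**The case against.** The strongest reply is that the sentence contradicts itself. It states 12 items, and the 32 to 224 range needs 32, so a careful programmer would find the gap before any score was produced. That stands as a limit on certainty: question 25 could be dropped, but it is not certain to be. It does not rescue the text, because a scoring rule should not depend on the programmer noticing that it is wrong.

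Two stronger readings are tempting, and the documents support neither.

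- A reader might infer that the IBDQ total is one item short, with a range of 31 to 217, and that the remission (> 170) and response (increase of at least 16 points, or > 170) endpoints in SAP Table 4 are therefore mis-scored. Both documents define the total from the individual questions, not from the four domain lists. With complete data these endpoints are unaffected. The 16-point rule is read here as applying to the total, because it is paired with a threshold of 170 that no domain can reach (the largest domain maximum is 84).
- A reader might infer that the change in the emotional subscore is wrong for every subject. The omission cancels wherever the answer to question 25 is the same at both visits.

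It is also fair to say that the reach is small. SAP Table 1 lists the IBDQ endpoints as exploratory. Section 8.1 plans only summary statistics for the subscores, and the repeated-measures model in section 6.4.2 refers to the IBDQ score without naming subscores. Nothing here touches the primary endpoint or the test of clinical remission.

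Finally, neither document reproduces the questionnaire or its scoring key. That question 25 belongs to emotional function follows by elimination. The inference is strong, but it should be checked.

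**Conclusion.** The scoring rule is wrong as written, and severity is low. The emotional function list has 11 items against 12 stated, and question 25 is in no domain. Followed literally, the list lowers the emotional subscore by 1 to 7 points at each visit for each subject with complete data. It distorts the change from baseline only where the question 25 answer moves, and it leaves an unanswered question 25 outside the imputation rule, the two-missing rule and Table 9. The total and its two responder endpoints are intact with complete data. They can be touched only through the missing-item cases worked above.

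This rests on three assumptions: that the list is programmed as printed, that items are scored 1 to 7 as the protocol says, and that question 25 is the twelfth emotional function item.

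**What to change.** Check the instrument's scoring key and, once confirmed, add question 25 to the emotional function list in SAP section 8.1. Add a programming check that the four domain lists cover questions 1 to 32 once each. With question 25 included, the counts become 10 + 5 + 12 + 5 = 32 and the domain sum runs from 32 to 224, as stated.

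The cost is one number in the SAP. If emotional subscores or IBDQ missing-item handling have already been programmed from the list, rerun them. SAP section 1 requires changes after approval to be documented in the clinical study report with the reason, and this correction can be recorded there.

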9 NUMBER AND TIMING OF ANALYSES

There will be a primary analysis after all subjects have completed 12-week IP. During the primary analysis, interim results from the OLE will be summarized descriptively. Complete analysis for the OLE will be covered in a different SAP.

10 CHANGES FROM PROTOCOL

Methods in this SAP different from the methods described in the protocol are summarized as follow:

- In Section 2, for objectives and endpoints that has accessing timepoint at Week 50, all timepoints at Week 50 were removed from this SAP. The final analysis of OLE data will be specified in a separate SAP.

- In Section 2 and Section 3.1, the definition for clinical response is refined so that responders will also include those patients who achieve clinical remission (CDAI < 150) but may not achieve ≥ 100 point reduction in CDAI from baseline.
- In section 2, additional exploratory endpoints (endoscopic remission, ulcer-free at Week 12, change in SES-CD segment score from baseline to week 12, clinical improvement by PRO-2 score, IBDQ remission or response,(steroid-free clinical remission for CDAI and by PRO-2, steroid-free clinical improvement by CDAI and by PRO-2, Clinical response by PRO-2 total score,) were add in the overall objectives and endpoints.
- In section 2, serum PD marker EHI was removed from the SAP. It will be analyzed when it becomes available.
- For analysis populations, PP analysis set was added.
- For evaluation of primary efficacy endpoint, the analysis specified in SAP V01 based on the method of multiple imputation was removed due to the known lack of sufficient correlation between SES-CD and CDAI scores in prior CD clinical trials. Instead, PP analysis set, which requires evaluable endoscopic score at Week 12, will be used and the confidence interval for the proportion will be calculated using Wilson-score method.
- Sensitivity analysis based on FAS was added to further access the robustness of primary analysis.
- For evaluation of secondary efficacy dichotomous or binary endpoint, the confidence interval for the proportion will be calculated using Wilson-score method, while non-responder imputation may apply for missing endpoint.
- For evaluation of the continuous secondary efficacy endpoint, PP analysis set and ANCOVA will be used for the change from baseline in SES-CD at Week 12. The median for the change from baseline in SES-CD score at Week 12 for PP analysis set will also be estimated and p-value for testing against no change will be reported using Wilcoxon rank test
- For evaluation of continuous exploratory efficacy endpoints, endpoints with multiple assessments over time, MMRM will be used. The 95% confidence interval for the LS mean for the change from baseline at Week 12 will be calculated.
- For evaluation of exploratory efficacy endpoint, proportion of subjects of meeting the definition will be calculated. For evaluation of continuous exploratory efficacy endpoints, MMRM method will be used, where appropriate.

11 REVISION HISTORY

Version	Effective Date	Reason
V01	28FEB2022	New
V02	19APR2022	Amendment

APPENDIX A. SIMPLE ENDOSCOPIC SCORE FOR CROHN'S DISEASE (SES-CD)

The Simple Endoscopic Score for Crohn's Disease (SES-CD) assesses the size of mucosal ulcers, the ulcerated surface, the endoscopic extension, and the presence of stenosis.

Variable	SES-CD Values			
	0	1	2	3
Size of ulcers	None	Aphthous ulcers (0.1 < 0.5cm)	Large ulcers (> 0.5 – 2cm)	Very large ulcers (> 2.0cm)
Ulcerated surface (%)	None	< 10%	10-30%	> 30%
Affected surface (%)	Unaffected segment	< 50%	50-75%	> 75%
Presence of narrowing	None	Single, can be passed	Multiple, can be passed	Cannot be passed

	Ileum	Right Colon	Transverse colon	Left colon	Rectum	Total
Presence and size of ulcers (0-3)						
Extent of ulcerated surface (0-3)						
Extent of affected surface (0-3)						
Presence and type of narrowings (0-3)						
Total SES-CD =						

Source: Daperno, et al. Gastrointest Endosc. 2004.

Note: Current Alimentiv scoring conventions are to be used.

APPENDIX B. CROHN'S DISEASE ACTIVITY INDEX (CDAI)

The Crohn's disease activity index (CDAI) scores range from 1 to approximately 600, with higher scores indicating more severe disease. Eight variables comprise the components of the CDAI score. Modification limits the contribution of the weight variable to no more than 10 points in negative contribution.

Clinical or laboratory variable	Weighting factor
Number of liquid or soft stools each day for 7 days	× 2
Abdominal pain (graded from 0 to 3 based on severity) each day for 7 days	× 5
General well being, subjectively assessed from 0 (well) to 4 (terrible) each day for 7 days	× 7
Complications*	× 20
Use of diphenoxylate or opiates for diarrhea	× 30
An abdominal mass (0 for none; 2 for questionable; 5 for definite)	× 10
Absolute deviation of hematocrit from 47% in men and 42% in women	× 6
Percentage deviation from standard weight	× 1

*One point is added for each set of complications: arthralgia or frank arthritis; inflammation of the iris or uveitis; erythema nodosum, pyoderma gangrenosum, or aphthous ulcers; anal fissures, fistulas, or abscesses; other fistulas; and fever (>100 °F) during the previous week.

Remission: CDAI score <150 points.

Moderate-to-severe disease: CDAI score 230–400 points.

APPENDIX C. PRO2 CALCULATION

The two CDAI items included in the PRO2 are daily stool frequency (SF) and abdominal pain (AP). SF consists of the number of liquid or very soft stools that occur per day. AP is rated on a 4-point scale (from 0 to 3) of increasing severity (Table a). This information is recorded by the subject on the electronic diary (or by paper diary if electronic diary not available). The average of the daily entries for the 7-day period prior to each visit is calculated and multiplied by weighting factors (X2 for SF and X5 for AP) to provide a total score for each component item. The total PRO2 score is the sum of the component item scores (Table b)

Table a. PRO2 Diary Card

	Day 1	Day 2	Day 3	Day 4	Day 5	Day 6	Day 7
Number of liquid or very soft stools per day							
Daily Abdominal Pain Rating (0 = none, 1 = mild, 2 = moderate, 3 = severe)							

Table b. Calculation of the Total PRO2 Score

	Total Component Item Score for 7 Days	Multiplication Factor	Total
Number of liquid or very soft stools per day		X 2	
Daily Abdominal Pain Rating		X 5	
		Total PRO2 Score	

Source: Khanna, et al. Aliment Pharmacol Ther. 2015.

APPENDIX D. PERIANAL DISEASE ACTIVITY INDEX (PDAI)

The perianal disease activity index (PDAI) score includes the evaluation of 5 elements:

- 1) discharge
- 2) pain
- 3) restriction of sexual activity
- 4) type of perianal disease
- 5) degree of induration

Each category is graded on a 5-point Likert scale ranging from no symptoms (score of 0) to severe symptoms (score of 4), with a range of 0 to 20; a higher score indicates more severe disease.

Item	Points
Discharge	
No discharge	0
Minimal mucous discharge	1
Moderate mucous or purulent discharge	2
Substantial discharge	3
Gross fecal soiling	4
Pain/restriction of activities	
No activity restriction	0
Mild discomfort, no restriction	1
Moderate discomfort, some limitation	2
Marked discomfort, marked limitation	3
Severe pain, severe limitation	4
Restriction of sexual activity	
No restriction of sexual activity	0
Slight restriction of sexual activity	1
Moderate limitation of sexual activity	2
Marked limitation of sexual activity	3
Unable to engage in sexual activity	4
Type of perianal disease	
No perianal disease	0
Anal fissure or mucosal tear	1
<3 perianal fistulas	2
>3 perianal fistulas	3
Anal sphincter ulceration or fistulas with significant undermining skin	4
Degree of induration	
No induration	0
Minimal induration	1
Moderate induration	2
Substantial induration	3
Gross fluctuance/abscess	4

APPENDIX E. GLOBAL HISTOLOGIC DISEASE ACTIVITY SCORE

Histological Variable	Description
Epithelial damage	0 normal 1 focal pathology 2 extensive pathology
Architectural changes	0 normal 1 moderately disturbed (< 50%) 2 severely disturbed (> 50%)
Infiltration of mononuclear cells in the lamina propria	0 normal 1 moderate increase 2 severe increase
Infiltration of polymorphonuclear cells in the lamina propria	0 normal 1 moderate increase 2 severe increase
Polymorphonuclear cells in epithelium	0 absent 1 in surface epithelium 2 cryptitis 3 crypt abscess
Presence of erosion and/or ulcers	0 no 1 yes
Presence of granuloma	0 no 1 yes
Number of biopsy specimens affected	0 none 1 < 33% (1 or 2 of 6) 2 33-66% (3 or 4 of 6) 3 > 66% (5 or 6 of 6)

Source: D'Haens, et al. Gastroenterology. 1998

APPENDIX F. ROBERTS HISTOPATHOLOGY INDEX

Histological Variable	Grading	Multiplication Factor
Chronic inflammatory infiltrate	0=No increase 1=Mild but unequivocal increase 2=Moderate increase 3=Marked increase	X1
Lamina propria neutrophils	0=None 1=Mild but unequivocal increase 2=Moderate increase 3=Marked increase	X2
Neutrophils in epithelium	0=None 1= < 5% crypts involved 2= < 50% crypts involved 3= > 50% crypts involved	X3
Erosion or ulceration	0=No erosion, ulceration, or granulation tissue 1=Recovering epithelium + adjacent inflammation 1=Probably erosion-focally stripped 2=Unequivocal erosion 3=Ulcer or granulation tissue	X5

Source: Mosli, et al. Gut. 2017.

APPENDIX G. SCHEDULE OF ASSESSMENTS – INDUCTION PERIOD

	Study Visit							Early Termination	NOTES
	Study Week	0	1	2	6	10	12		
	Study Day	1	8	15	43	71	85		
Visit window (days)	0	±1	±3	±3	±3	±3			
Procedure									
Eligibility Confirmation	X								
Randomization	X								Via IRT system
Complete Physical Examination						X	X		
Targeted Physical Examination	X		X	X	X				
Vital Signs	X	X	X	X	X	X	X		Heart rate, temperature, blood pressure; Take pre-dose (no more than 30 minutes pre-infusion), end of infusion, and end of observation period.
Weight	X	X	X	X	X	X	X		Needed for CDAI assessment
ECG	X					X	X		
Adverse Events Assessment	X	X	X	X	X	X	X		
Concomitant Medication	X	X	X	X	X	X	X		
Efficacy Assessments									
Ileocolonoscopy with Biopsy						X	X		Ileocolonoscopy to be performed within 10 days after Week 12 visit, or at early termination visit
Review eDiary Data from Subjects	X	X	X	X	X	X	X		Remind subjects to record in their eDiary daily
CDAI Assessment	X	X	X	X	X	X	X		
PDAI	X					X	X		
Fistula Drainage Assessment	X		X	X	X	X	X		
IBDQ	X			X		X	X		
Laboratory Testing									
CBC	X	X	X	X	X	X	X		
Chemistry Panel	X		X	X		X	X		
Fasting Lipid Panel	X					X	X		
Urinalysis	X		X	X		X	X		

	Study Visit							Early Termination	NOTES
	Study Week	0	1	2	6	10	12		
	Study Day	1	8	15	43	71	85		
Visit window (days)	0	±1	±3	±3	±3	±3			
Procedure									
Urine Pregnancy Test (WOCBP only)	X			X		X	X		
Pharmacokinetics	X ^a	X	X ^b	X ^b	X ^a	X	X		a. The PK sample at Week 0/Day 1 and Week 10 must be taken pre-dose, immediately following the end of infusion (within 30 minutes), and 1 hour after the end of infusion. b. The PK sample taken at Weeks 2 and 6 must be taken pre-dose (within 30 minutes prior to dosing).
Immunogenicity	X ^a		X ^a	X ^a		X	X		^a To be taken pre-infusion
Biomarkers									
Biomarkers	X		X	X	X	X	X		Serum at all visits; additional whole blood at Weeks 0, 6 and 12
Soluble TL1A	X		X	X	X	X	X		
hsCRP	X	X	X	X	X	X	X		
Fecal Calprotectin	X			X		X	X		
Infusion	X		X	X	X				Include date, start and stop time, volume infused, and length of the IV infusion. Infusion observation period at Week 0/Day 1 and Week 2 will be 1 hour (2 hours for subjects in Czech Republic); 30 minutes for all subsequent infusions thereafter.

